12.1 STUDY INFORMATION

12.1.1 Protocol

Study No.: WLI-1196-PER

Clinical Investigation - Lima Peru

1. **Title:** Efficacy and Safety Investigation of SeraSeal
2. **Principal Investigator: Thoracic & Cardiovascular:** [name]
[name]
[name] [name]
[name]
[name]
General Surgery: [name]
[name]
[name]
[name]
[name]
[name]
[name]
[name]
[name]
Head & Neck: [name]
[name]
Orthopedics: [name]
Neurosurgery: [name]
3. **Monitors:** [name]
Edgardo Rebagliati Martins National Hospital

[name] [name]
Edgardo Rebagliati Martins National Hospital
4. **This protocol focuses on treatment**
5. **Location:** Edgardo Rebagliati Martins National Hospital, Lima, Peru
Guillermo Almenara I. EsSalud National Hospital, Lima, Peru
[name] Casimiro Ulloa Emergency Hospital
FAP- Peruvian Air Force Hospital, Lima, Peru
Military Hospital of Peru, Lima
6. **Research Plan:**

6.1 Purpose: The purpose of this study is to investigate the safety and effectiveness of SeraSeal on clotting time in surgical or trauma wounds. This study is designed to determine whether it is safe and effective in achieving hemostasis in different types of wounds.

6.2 Hypothesis or Research Questions or Objectives: The null hypothesis is that cauterization is more effective than SeraSeal in achieving hemostasis. The alternative hypothesis is SeraSeal will achieve hemostasis sooner than cauterization. A secondary endpoint is the measurement of blood loss.

6.3 Significance: SeraSeal shows promise of being an effective hemostatic agent applicable to wounds, surgical operations in which hemostasis is difficult (hepatic, renal and splenic trauma, debridement, burns, skin grafting, endoscopic procedures), control of epistaxis, esophageal variceal bleeding, bleeding peptic ulcers, and bleeding associated with proctitis and cystitis. For some of these conditions, there is no entirely satisfactory treatment.

6.4 Relevance: The availability of an easy to use, stable, safe, effective hemostatic agent, would be a tremendous advantage to the trauma patient (surgical or accidental), possibly reducing morbidity and mortality significantly, and conserving surgical and blood resources.

6.5 Background and Review of Literature:

Problem with Bleeding Wounds

Bleeding is still a major cause of morbidity and mortality in wounds. Thirteen percent of patients suffering acute trauma, die of bleeding¹. Of the total deaths occurring on the battlefield, eight-five percent are due to blood loss². Particularly vulnerable areas are the face, groin, pelvis and extremities, areas not protected by body armor. In head and neck trauma, uncontrolled bleeding can cause airway compromise and asphyxiation³. In trauma survivors, inability to control bleeding leads to blood transfusion, increased complication rates, immunosuppression, inability to generate red blood cells, and prolonged time in the hospital. The ideal solution to these problems is to control the bleeding in the first place. The limiting factor in performing burn debridement of chronic wounds results in bleeding, which is essentially an end point for debridement, because there is no satisfactory way of controlling bleeding in granulation tissue. This results in repeated debridement. Bleeding is a major cause of skin graft loss and flap necrosis. Outside of the hospital, the paramedic has only compresses to control bleeding. A quick, effective, and safe device to control bleeding, would be extremely beneficial.

Hemostatic agents in wounds

Commercially available topical thrombogenic agents include microfibrillar collagen (Avitene®), collagen sponges (Gelfoam®, Instat®), and fibrin sealants (Tisseel®, AFTA®, ViGuard®). Topical collagen preparations have been available for more than 25 years and have a limited ability to facilitate clotting. When hemorrhage is excessive or the patient's clotting factors are inhibited, they are less effective.

Fibrin Sealants

These are prepared from homologous, pooled human or bovine fibrinogen, Factor XII, and thrombin that must be combined to make the fibrin. Other components include calcium to provide activation of Factor XIII, fibronectin to aid in adhesion, and an inhibitor of fibrinolysis to prolong fibrin clot life. Fibrin sealants have shown great promise in controlling wound hemorrhage. Fibrin sealants have been shown to reduce operating time, blood loss, and do not appear to interfere with healing⁴. When applied to a ballistic wound as a dry dressing, the sealant reduced blood loss by 64%⁵.

Problems with current tissue sealants

Several problems exist with the commercially available fibrin sealants: They are a two part system of fibrin and thrombin, which must be mixed at operation or trauma setting, adding to the operative time and delaying transportation to a stable operative setting. Previously, the FDA withheld approval from European products because they used pooled human plasma as a product source⁶. The fibrin sealants are somewhat difficult to use, as they must be mixed from four components, a process which takes approximately 15 minutes, and then must be used within four hours. If they are to be used endoscopically, they must be placed through a dual luman catheter and mixed in situ⁷. Their viscosity makes application difficult via catheters and in small areas, and limits methods of application such as sprays, or foams, which would be useful for large wounds. The time between mixing and hemostasis can be

several minutes, typically 3-5 minutes, further slowing operation repair⁸. The incorporation of fibrin sealants into a dry dressing has reduced some of these problems. The strength of the clot formation, when utilizing a dry dressing, can be sub-optimal. These shortcomings limit the utility of fibrin sealants for hemostasis in the battlefield, emergency response teams such as paramedics, and in the surgical arena.

Bovine topical thrombin in most cases, is a heterologous plasma thrombin concentrate that has been used for hemostasis since the 1940's. Some commercial bovine thrombin preparations are highly immunogenic, and appear to be associated with an increased risk for adverse clinical outcomes during subsequent surgical procedures⁹. Antibody formation and anaphylaxis (rates 0.5 to 5.8%) have also been seen with Factor V and aprotinin, a polyvalent proteinase inhibitor isolated from bovine lungs, and used alone to enhance clot stability, or in combination with fibrin sealants^{10,11,13}. These antibodies may interfere with the heparin anti-Xa assay, thereby complicating the monitoring of anticoagulant therapy¹². The commercially available product, Tisseel VH fibrin sealant, contains bovine aprotinin, resulting in the risk of hypersensitivity.

What this study will determine

This study is designed to determine whether SeraSeal is safe, effective, and will improve the quality of care, in achieving hemostasis in surgical wounds or other emergent hemorrhagic episodes. The effectiveness will be determined by achieving hemostasis after application of the product. The safety will be determined by monitoring outcomes from application: recurrence of bleeding, infection, lack of healing, and presence of hypersensitivity reactions, e.g. pruritus, fever, rash, anaphylaxis. An improved quality of care will be achieved by reducing or eliminating the hospital length of stay.

Characteristics of SeraSeal

SeraSeal is a bovine protein-derived accelerator of hemostasis interacting with the intrinsic and extrinsic pathways. It is obtained from pathogen and prion free cows. SeraSeal can be provided as a solution, spray, foam, incorporated into an absorbable dressing or a non-absorbable removable dressing. Its active ingredients are the bovine proteins Factors II, VII, IX, and X.

Toxicity of SeraSeal

A total dosage level of SeraSeal over 13,000 IU/Kg (2.4 mg protein) in leporids and canines had no adverse effects¹⁴. The total expected treatment levels to be used in this study is less than 1,000 IU/Kg, a 130 fold lower level than the no toxic effect. Cell culture studies reveal that SeraSeal is not directly toxic for any cells tested. Thus, drug related toxicity is not expected to be seen in this clinical study.

6.6 Research Design and Methods: This clinical trial will be a difference study where SeraSeal will be used as a liquid, administered by a syringe (300 IU/0.1ml), and compared to standard surgical technique as the control. Patients receiving treatment at Edgardo Rebagliati Martins Hospital, the National Guillermo Hospital, Peruvian Air Force Hospital, and the Military Hospital of Peru will serve as study volunteers. Prior to enrollment in the study, an initial screening test and subsequent studies will take place, including: informed consent, collection and recording of subject demographic information, medical history, current medications, assessment of inclusion/exclusion criteria, physical examination, with blood draws for hematological assessment and coagulation studies for bleeding and time to hemostasis. The location of the study wounds will be invasive. The study wound sites will involve bone and soft tissue.

This is a single-blinded, parallel, randomized clinical trial, where the primary endpoint is hemostasis. Secondary endpoints will include reduction of blood loss, fewer blood transfusions. There are 18 designated surgical faculty members from Head & Neck, Vascular, Thoracic Cardiovascular, Neurosurgery, Orthopedics, and General Surgery participating in this study, with a minimum of 10 surgical procedures being studied. All of the participating surgeons are highly skilled and have extensive expertise in their surgical specialty.

Randomization: The patients will be randomized within each surgical department by drawing a SeraSeal or Cauterization slip. Which ever slip is drawn the next participating patient having the same surgical procedure will

be given the opposite method to control bleeding at same specific bleeding wound sites.

In this trial, the dosage level of SeraSeal is 3,000 IU/ml, with a maximum expected dosage of 10,000 IU, 50 times less than the pre-clinical toxicity studies¹⁴. After hemostasis is achieved the excess SeraSeal will either be removed through irrigation and suction or absorption onto a surgical sponge. Blood loss will be measured and recorded by reading the volume in the suction canister, or by weighing the blood soaked surgical sponges (1 ml whole blood = 1.04 g). A time to hemostasis is measured from the time when the product or the control is first applied to the wound, until no bleeding or oozing is observed for the entire wound. A nurse will use a stopwatch to record the time to hemostasis. SeraSeal is expected to achieve hemostasis 25% faster than the control. Stopping criteria for treatment in the investigational group will be when hemostasis fails to be achieved within 10 minutes for a particular wound, or at the discretion of the surgeon. If this should happen, the patient will be switched over to standard surgical practices. There are no stopping criteria for the control, since the control employ standard surgical procedures.

The patients will be monitored for 30 days, and will be measured by the amount of post-operative bleeding and overall wound healing for those wounds that can be observed. A base line hemoglobin (HGB) and hematocrit (HCT) blood count, prothrombin time (PT), partial thromboplastin time (PTT), will be drawn and measured 24 hours, and also at 48 hours after surgery. The HGB, HCT, PT and PTT will be drawn 30 days after surgery (Table 1). The patients will be observed and assessed for a minimum of 60 minutes after application of SeraSeal for signs of hypersensitivity to the investigational product, and throughout the 30 days. They will be assessed for, but not limited to, skin rash; wheezing; anaphylaxis; pruritus; prolong coagulation tests; delayed healing or infection through quantitative cultures. In the event there is progression of edema leading to respiratory distress, anaphylaxis, or shock due to blood loss, a crash cart and/or any additional standard and customary treatment(s), will be available. This study will not limit the standard of care performed at both investigational hospitals. The following components of wound care are "standard practice" at each of the hospitals: daily dressing changes; quantitative cultures when infection may be present; routine blood tests. All enrolled study subjects may request to be withdrawn from the study at any time, and will be terminated from the study and provided standard of care. All adverse events will be recorded according to whether the event was unrelated, unlikely, possibly or probably related to the study treatment.

Table 1: Schedule of Assessments

Test	Pre-Op	Surgery	24 Hrs Post Op	48 Hrs Post Op	30 Days
Medical History	X				
Physical Examination	X				
Informed Consent	X				
Designated Delivery System		X			
HGB	X		X*	X+	X
HCT	X		X*	X+	X
PT	X		X*	X+	X
PTT	X		X*	X+	X
ECG	X				
X-Ray Work-UP	X				
Wound care			X	X+	
Microbiological work-up			X*	X+	
Adverse Events			X	X	
Primary Variable		X	X	X	
Secondary Variable		X	X	X	
Safety					
Adverse Events		X	X	X+	X

* measured as often as needed

+ monitored beyond 48 hours as needed

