8.0 Data Analysis:

8.1 Data Collection: There will be one study form for each patient. The surgery form will have all of the outcome data, including blood loss and complications. Once a patient is placed on the surgery schedule, the patient will be asked to participate in the clinical trial by the participating investigator surgeon. The only patients that will require special action are the SeraSeal patients. For those patients the need for SeraSeal will be made known only to the attending surgeon and/or fellows, and made available to the OR room. At the time of the pre-op exam, the inclusion/exclusion of participation in the study will be filled out. The research nurse will collect all data forms and will be responsible for evaluating them for completeness and accuracy, except for time to hemostasis supplied by the surgeon.

8.2 Statistical Analysis: We will compare continuous outcomes such as time to hemostasis (primary outcome), pre and post operative blood loss, surgery duration, (log) bacterial titer, and length of hospital stay in SeraSeal versus conventional treatment, using factorial analysis of variance (ANOVA) methods.

For continuous lab outcomes measured on four occasions (base, 24 hours, 48 hours, 30 days), we will use repeated measure analysis of variance methods to compare mean lab values for conventional versus SeraSeal overall.

For binary outcomes, (including adverse event outcomes) that are not quantified or that may be dichotomized for clinical convenience and interpretability such as fever (yes or no) or pruritus (yes or no) we will use chi-square methods to compare conventional versus SeraSeal treatment proportions overall. Since the total follow up times may differ between groups, we will also compare rates per person-time of binary outcomes under conventional versus SeraSeal treatment overall.

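### About half of the treatment assignments follow by rule from the previous patient's, with no concealment described, so a recruiting surgeon who knows the previous arm knows the next one

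*Protocol*

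**What the plan says.** Protocol section 6.6 describes the design thus: "This is a single-blinded, parallel, randomized clinical trial, where the primary endpoint is hemostasis". Allocation has two steps. The first is a chance draw: "The patients will be randomized within each surgical department by drawing a SeraSeal or Cauterization slip". The second is a rule. It names the patient ("Which ever slip is drawn the next participating patient having the same surgical procedure will") and then the arm: that patient is to "be given the opposite method to control bleeding at same specific bleeding wound sites". The text does not say whether a fresh slip is drawn after each pair or whether one draw starts an alternation that then continues. It also does not say whether a department means one hospital's department or a specialty across hospitals.

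Section 8.1 describes recruitment. Once a patient is on the surgery schedule, "the patient will be asked to participate in the clinical trial by the participating investigator surgeon". On knowledge of the arm, it says that for SeraSeal patients "the need for SeraSeal will be made known only to the attending surgeon and/or fellows". Section 7.0 says that subjects are selected at random within each participating department, but gives no procedure for doing so. Nowhere does the Protocol mention sealed envelopes, central allocation, an independent holder of the slips or any other concealment.

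**The concern.** Randomisation protects a comparison only if the person enrolling a patient cannot foresee that patient's arm. Here the second patient of each pair gets whatever the first did not. The surgeon cannot be blind to the treatment used, and the same role issues the invitation. A surgeon who knows the next arm can, without intending to, invite an easier bleed when SeraSeal is due and a harder one when cautery is due.

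There is room for this. Section 6.7 admits all ages, patients on anticoagulants and patients with coagulation disorders, so expected bleeding varies widely. Its similarity criterion for wounds points to a list in Table 1, but Table 1 is the schedule of assessments and lists no wounds. The primary outcome is also exposed. Section 6.6 has a nurse time hemostasis with a stopwatch, while section 8.1 has the research nurse check all data "except for time to hemostasis supplied by the surgeon". That inconsistency is a separate matter, but it means that foreknowledge, treatment and outcome may rest with one person.

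**Working it through.** **Inputs from the Protocol.** Total N = 200 (section 6.9). At least 10 procedures (section 6.6). 20 per group, 80% power, two-sided 0.05, a mean of 30 minutes reduced to 22.5 (section 8.2, sample size). The Protocol gives no figure for the predictability of allocation.

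**The plan's own figure.** 20 × 2 × 5 = 200 reproduces, which is 100 per arm. No SD is stated. Solving the two-sample t power formula for 80% power with 20 per group and a difference of 7.5 minutes gives an SD of about 8.25 minutes (8.47 by the normal approximation). This is used below only to turn SD units into minutes.

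**Share of assignments determined by the previous one.** Let S be the number of procedure strata.

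- New slip for each pair, all pairs complete: 100/200 = 50%.
- New slip for each pair, every stratum ending on an unpaired patient: (200 − S)/2/200. With S = 10 this is 95/200 = 47.5%; with S = 20 it is 90/200 = 45%.
- One draw per stratum, then continued alternation: (200 − S)/200. With S = 10 this is 190/200 = 95%; with S = 20 it is 180/200 = 90%.

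Under complete pairs, someone who always knows the previous arm guesses correctly 0.5 × 0.5 + 0.5 × 1 = 75% of the time, against 50% under unpredictable 1:1 allocation.

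**What steering could do (illustration, pair reading).** Assumptions not in the documents: no true effect; a fraction k of the determined assignments is known to the recruiter; each known patient's expected time is shifted by η SD in SeraSeal's favour, down in the SeraSeal arm and up in the control arm. Half of each arm is determined, so the bias is 0.5kη + 0.5kη = kη. With 100 per arm the standard error is √(2/100) = 0.141 SD. The rejection rate is 1 − Φ(1.96 − kη/0.141) + Φ(−1.96 − kη/0.141).

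| k | η (SD) | Bias (SD) | Bias/SE | Rejection rate under the null |
|---|---|---|---|---|
| 1 | 0.25 | 0.25 | 1.77 | about 42% |
| 1/2 | 0.25 | 0.125 | 0.88 | about 14% |
| 1/4 | 0.25 | 0.0625 | 0.44 | about 7% |
| 1 | 0.20 | 0.20 | 1.41 | about 29% |
| 1 | 0.10 | 0.10 | 0.71 | about 11% |
| 0 | any | 0 | 0 | 5% |

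In minutes, 0.25 × 8.25 ≈ 2.1, set against the planned difference of 7.5. The SD behind that conversion comes from a liver-surgery calculation and may not describe all departments pooled. The calculation uses a simple two-arm test rather than the factorial ANOVA of section 8.2.

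**The case against.** The strongest reply is that determined is not the same as known. The Protocol says "There are 18 designated surgical faculty members", and section 7.0 names four recruiting hospitals. The next patient with the same procedure may come to a surgeon who did not treat the previous one, and section 8.1 limits knowledge of SeraSeal patients to the attending surgeon and fellows. This stands. A reader might infer that at least half of all assignments are known in advance to the recruiter, but the documents do not support that. The share known is not stated and could be well below the share determined, which itself falls slightly under half when pairs stay open. Still, someone must know the previous arm for the rule to be applied, and nothing withholds it from the next recruiter.

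A reader might also infer that the surgeon controls scheduling and decides which wound counts as the same site. The text says neither. It places scheduling before the invitation without naming who does it, and leaves the choice of wound unassigned. Section 7.0's random selection, the pairing within procedure and the wound-similarity criterion all point towards less freedom to steer. They weaken the concern without removing it: the first has no mechanism, and the last refers to a list that is not there.

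Finally, it would go too far to say that the trial cannot be called randomised. Under the pair reading the first patient of each pair is drawn by chance, and an analysis of those patients alone would keep that protection, provided the draw follows enrolment. It would use about half the sample, and section 8.2 does not plan it.

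**Conclusion.** The point holds. As written, about half of assignments (47.5% to 50% with 10 procedures and a new slip per pair; about 95% under continued alternation) follow from the previous patient's arm. The unblinded surgeon who invites patients can foresee the next arm whenever the previous one is known to him or her, and no concealment is described. Selection bias is possible, and adjustment cannot reliably remove steering on difficulty that was never recorded. A statistical analysis plan could not undo an allocation rule.

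The structural finding rests on the text alone. The error rates are illustrations. The 42% figure requires that every determined assignment is known and steered by 0.25 SD; at the same shift it drops to 14% or 7% if only a half or a quarter are known. Nothing in the documents shows that steering would occur or how large it would be. The rule should nevertheless be changed before enrolment, because the harm cannot be repaired afterwards.

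**What to change.** In section 6.6, delete the opposite-method rule. Replace it with a computer-generated list, stratified by department, in permuted blocks of randomly varying size, prepared by someone who does not recruit. Release each assignment through sequentially numbered, opaque, sealed envelopes or an equivalent system, and only after consent, eligibility and the target wound have been recorded. Say whether a department is counted within or across hospitals. Bring section 8.1 into line, since its arrangement for having SeraSeal ready in the operating room presumes that the arm is already known. Adjust for procedure in the analysis.

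The cost is a short amendment to two sections, a list, a set of envelopes and minor changes to operating-room logistics. Arms may be slightly unequal within rare procedures, which adjustment for procedure can handle. Stratifying by department rather than by each procedure limits the number of incomplete blocks.

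### Blood loss is read from canister or sponges with no deduction for irrigation fluid or dry sponge weight, so any extra irrigation in the SeraSeal arm counts as blood

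*Protocol*

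**What the plan says.** Blood loss is a declared endpoint. Protocol section 6.2 states: "A secondary endpoint is the measurement of blood loss". Section 6.6 states: "Secondary endpoints will include reduction of blood loss, fewer blood transfusions".

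The measurement rule is in section 6.6: "Blood loss will be measured and recorded by reading the volume in the suction canister, or by weighing the blood soaked surgical sponges", with the conversion "1 ml whole blood = 1.04 g". The sentence just before it deals with the investigational product: "After hemostasis is achieved the excess SeraSeal will either be removed through irrigation and suction or absorption onto a surgical sponge". The dose is given in the same paragraph: "the dosage level of SeraSeal is 3,000 IU/ml, with a maximum expected dosage of 10,000 IU". The control is standard surgical technique, and no removal or irrigation step is described for it.

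Table 1 schedules the secondary variable at surgery, 24 hours and 48 hours, and has no entry for it in the pre-operative column. Section 8.2 lists, among the continuous outcomes to be compared between arms by factorial ANOVA, "pre and post operative blood loss, surgery duration".

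**The concern.** Both ways of removing excess product lead to the places from which blood loss is read: suction fills the canister, and sponges are weighed. The rule has no term that takes irrigation fluid out again. If SeraSeal wounds receive more irrigation than control wounds, the extra fluid is recorded as blood in one arm and shifts the difference between arms. That could hide or reverse a real reduction in blood loss.

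Two further gaps affect both arms. No dry sponge weight is deducted. The word joining the two sources also lets one of them stand for the total, with no rule for choosing, although a case can put blood into both. Some of those in theatre know the allocation (section 8.1), so an open choice of source is undesirable.

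Section 8.2 then names a quantity that precedes treatment and does not name the intra-operative loss that section 6.6 measures.

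This is a bedside measurement. An irrigation volume or dry weight that was not recorded in theatre cannot be recovered by a later analysis plan.

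**Working it through.** **Inputs from the protocol.** Concentration 3,000 IU/ml and maximum expected dose 10,000 IU (6.6); density 1.04 g/ml (6.6); 20 per group in each of 5 departments (8.2), so 20 × 5 = 100 per arm. The protocol gives no blood-loss mean or SD, no irrigation volume and no sponge weight, so it has no figure of its own to reproduce for this endpoint. The 200-patient calculation concerns time to hemostasis and is not affected.

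**1. Product volume.** 10,000 / 3,000 = 3.3 ml at most. This is negligible, so where product is removed by sponge alone the arm-specific error is trivial.

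**2. Irrigation.** Let M be the true control mean, r the true proportional reduction and W the net uncorrected irrigation fluid (SeraSeal arm minus control arm).

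- Observed SeraSeal mean = (1 − r)M + W
- Observed reduction = r − W/M
- The effect vanishes when W = rM

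Take r = 25% as an assumption; it is the protocol's target for time to hemostasis, not for blood loss. M and W are also assumed.

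| M (ml) | W = 50 ml | W = 100 ml | W that cancels the effect |
|---|---|---|---|
| 200 | 25% − 25% = 0% | 25% − 50% = −25% (apparent increase) | 50 ml |
| 300 | 25% − 16.7% = 8.3% | 25% − 33.3% = −8.3% (apparent increase) | 75 ml |
| 500 | 25% − 10% = 15% | 25% − 20% = 5% | 125 ml |

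**3. Power under the same assumptions.** Take M = 500 ml, SD = 250 ml (half the mean, assumed), 100 per arm, two-sided 5%. Power = Φ(δ / (SD√(2/n)) − 1.96), with SD√(2/n) = 250 × √0.02 = 35.4 ml.

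- W = 0: δ = 125, 3.54 − 1.96 = 1.58, power 94%
- W = 50: δ = 75, 2.12 − 1.96 = 0.16, power 56%
- W = 100: δ = 25, 0.71 − 1.96 = −1.25, power 11%

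**4. Dry sponge weight, both arms.** For an assumed 5 to 20 g per dry sponge, 5/1.04 = 4.8 ml and 20/1.04 = 19.2 ml of false loss each. Ten sponges give 50/1.04 = 48 ml to 200/1.04 = 192 ml.

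**5. One source instead of two, both arms.** If blood divides evenly between canister and sponges (assumed), reading only one records half of the loss.

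**6. Section 8.2 against Table 1.** Table 1 collects the secondary variable at surgery, 24 hours and 48 hours. Section 8.2 names pre-operative and post-operative loss. The pre-operative item has no scheduled collection, and the surgical item that is collected is not named.

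**The case against.** The best reply is that the protocol is silent rather than wrong. Control wounds may well be irrigated under standard technique. The text does not say that the canister is read after the wash; that order is inferred from two adjacent sentences. A factor for whole blood suggests net blood weight, so a dry-weight deduction may be intended. The two sources may simply be the method for each collection route, not alternatives. Sites may deduct irrigation by custom. The list in 8.2 is introduced as examples, and Table 1 plans collection at surgery.

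Much of this stands, and it limits the point. A reader might infer that 50 to 500 ml of wash fluid is added to every SeraSeal patient and to no control patient. The documents do not support that: no volume is given, control irrigation is not excluded, and one of the two removal routes involves no wash. Nor do they support calling blood loss the main secondary endpoint, since it is named but not ranked. Saying that the comparison does not measure blood loss at all would also go too far, because the error is additive and of unknown size. Intra-operative loss is not shown to be left out of the analysis; section 8.2 is badly worded on it.

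What the reply does not remove is the missing rule. The protocol lists five hospitals and states no common deduction. It writes a wash into one arm only and gives no instruction to combine the sources. Local custom cannot ensure like-for-like readings between arms.

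**Conclusion.** The point holds as a measurement defect in a named secondary endpoint. Followed as written, any net excess of irrigation fluid in the SeraSeal arm is counted 1:1 as blood and biases the comparison against SeraSeal. The bias is the difference between arms in uncorrected fluid. The direction given assumes that the wash written for SeraSeal is not matched in control. Its size cannot be computed from the protocol; the reductions and power figures above are illustrations on assumed means, SD and volumes. The only document-based quantity, product volume, is at most about 3.3 ml and does not matter.

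The missing dry-weight deduction and the choice of source cause overcounting, undercounting and noise in both arms. They are not evidence of a difference between arms. The pre-operative item in section 8.2 is a wording conflict with Table 1. The primary endpoint and sample size are untouched.

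**What to change.** In section 6.6, define intra-operative blood loss identically for both arms:

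(canister volume − recorded irrigation volume) + (wet − dry sponge weight) / 1.04

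Both sources are always summed. Because of that, irrigation fluid taken up by sponges is also deducted, apart from a small difference in density.

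Reading the canister before the SeraSeal wash is not a good substitute. With no matching cut-off in control, it would leave out blood rinsed from the wound in one arm only and could create a bias in the other direction.

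In section 8.2, replace pre-operative and post-operative blood loss by intra-operative and post-operative blood loss, in line with Table 1.

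The cost is a wording change and two extra entries per case, irrigation volume and dry sponge weight. No stated number changes.
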